7.1.2. Definition of an Adverse Reaction

An adverse reaction means any adverse event caused by a drug. Adverse reactions are a subset of all suspected adverse reactions for which there is reason to conclude that the drug caused the event.

7.1.3. Definition of Unexpected Adverse Event or Unexpected Suspected Adverse Reaction

An adverse event or suspected adverse reaction is considered “unexpected” if it is not listed in the Investigator’s Brochure or is not listed at the specificity or severity that has been observed. For example, under this definition, hepatic necrosis would be unexpected (by virtue of greater severity) if the Investigator’s Brochure referred only to elevated hepatic enzymes or hepatitis. “Unexpected,” as used in this definition, also refers to TEAEs or suspected adverse reactions that are mentioned in the Investigator’s Brochure as occurring with a class of drugs, or as anticipated from the pharmacological properties of the drug, but are not specifically mentioned as occurring with the particular drug under investigation. For example, although angioedema is anticipated to occur in some patients exposed to drugs in the Angiotensin-Converting Enzyme (ACE) inhibitor class and angioedema would be described in the Investigator’s Brochure as a class, the first case of angioedema observed with the drug under investigation should be considered unexpected for reporting purposes.

This definition relies entirely on a listing of the adverse events or suspected adverse reactions in the Investigator’s Brochure as the basis for determining if newly acquired information generated from clinical trials or reported from other sources is unexpected. The suspected adverse reactions listed in the Investigator’s Brochure (i.e., “expected”) are those observed with the investigational drug and for which a causal relationship between the event and the drug is suspected or confirmed.

7.1.4. Definition of a Serious Adverse Event or Serious Suspected Adverse Reaction

A TEAE or suspected adverse reaction is considered “serious” if, in the view of either the Investigator or Sponsor, it results in any of the following outcomes:

- a. Death.
- b. A life-threatening TEAE.
 - *A TEAE or suspected adverse reaction is considered “life-threatening” if, in the view of either the investigator or sponsor, its occurrence places the patient at immediate risk of death. It does not include a TEAE or suspected adverse reaction that, had it occurred in a more severe form, might have caused death.*
- c. Inpatient hospitalization or prolongation of existing hospitalization.
 - *Hospitalization for elective treatment of a pre-existing condition that did not worsen during the study is not considered a TEAE.*
 - *Complications that occur during hospitalization are TEAEs. If a complication prolongs hospitalization, the event is an SAE.*
 - *“Inpatient” hospitalization means the patient has been formally admitted to a hospital for medical reasons. This may or may not be overnight. It does not include presentation at a casualty or emergency room.*
- d. A persistent or significant incapacity or substantial disruption of the ability to conduct normal life functions.
 - *This is not intended to include experiences of relatively minor medical significance such as uncomplicated headache, nausea, vomiting, diarrhea, influenza, accidental*

trauma (i.e., sprained ankle) that may interfere or prevent everyday life functions but do not constitute a substantial disruption.

- e. A congenital anomaly in the offspring of a patient who received drug.
- f. Important medical events that may not result in death, be life-threatening, or require hospitalization may be considered serious when, based upon appropriate medical judgment, they may jeopardize the patient and may require medical or surgical intervention to prevent one of the outcomes listed in this definition. Examples of such medical events include allergic bronchospasm requiring intensive treatment in an emergency room or at home, blood dyscrasias or convulsions that do not result in patient hospitalization, or the development of drug dependency or drug abuse.
 - Medical and scientific judgment should be used in deciding whether prompt reporting is appropriate in this situation.

Seriousness (not severity) serves as a guide for defining regulatory reporting obligations. An SAE is not necessarily severe (e.g., an overnight hospitalization for a diagnostic procedure must be reported as an SAE even though the occurrence is not medically serious). Similarly, a severe AE is not necessarily serious (e.g., nausea lasting for several hours may be rated as severe but may not be considered serious).

7.2. Adverse Device Effect and Serious Adverse Device Effect

An Adverse Device Event (ADE) is defined as any untoward and unintended response to a medical device. In this case, an ADE would refer to any untoward and unintended response to the RS00 Model 8 DPI.

A Serious Adverse Device Effect (SADE) is an adverse device effect that has resulted in any of the consequences characteristic of a serious adverse event or that might have led to any of these consequences if suitable action had not been taken or intervention had not been made or if circumstances had been less opportune.

A device event may also be a SAE if the product involved a participant in the clinical trial. A test article (device) that malfunctioned prior to use in a clinical research participant would not be a SAE for the participant. However, if the device malfunctioned or broke once use was attempted by the participant; it would be reportable as an AE, or as a SAE if serious criteria were met.

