5.2.3. Storage and Handling

All study drug will be kept in a locked area with limited access and stored at 15°-30°C (59°-86°F). When in the possession of patients, all study drug should be stored in a cool, dry area. Study drug is packaged, per strength, as four capsules per bottle, with eight bottles and two DIs per box.

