7.1. Definition of a Treatment-Emergent Adverse Event

An AE is any untoward medical occurrence associated with the use of a drug in humans, whether or not considered drug related. All AEs that occur after the time of treatment with the investigational product will be considered a Treatment Emergent AE (TEAE).

A TEAE can be any unfavorable and unintended sign (e.g., an abnormal laboratory finding), symptom, or disease temporally associated with the use of a drug, without any judgment about causality.

A TEAE **does** include any:

- Exacerbation of a pre-existing illness.
- Increase in frequency or intensity of a pre-existing episodic event or condition.
- Condition detected or diagnosed after study drug administration even though it may have been present prior to the start of the study.

- Continuous persistent disease or symptoms present at baseline that worsen following the start of the study.
- Events considered by the investigator to be related to study-mandated procedures.
- Abnormal assessments (e.g., change in physical examination), if they represent a clinically relevant finding, that were not present at Baseline or worsened during the course of the study.
- Laboratory test abnormalities, if they represent a clinically relevant finding, symptomatic or not, which were not present at Baseline or worsened during the course of the study.

A TEAE **does not** include a/an:

- Medical or surgical procedure (e.g., surgery, endoscopy, tooth extraction, transfusion); the condition that leads to the procedure is an AE.
- Situations where an untoward medical occurrence has not occurred (e.g., hospitalization for cosmetic elective surgery, social and/or convenience admissions).
- Overdose of either study drug or concurrent medication without any signs or symptoms.
- Hospitalization for elective treatment of a pre-existing condition that did not worsen during the study is not considered an AE.

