7.4. Assessment of Relatedness to Study Drug or Device

The Investigator will assess each TEAE and ADE for causality based on their medical judgment and the observed symptoms associated with the event. Each TEAE and ADE will be assessed as related or unrelated to study drug based on the following criteria:

- Unrelated This category applies to those TEAEs and ADEs that the Investigator determines are most likely due to extraneous causes (disease, environment, etc.) and does not follow a reasonable temporal relationship.
- Related This category applies to those TEAEs and ADEs that the Investigator determines are most likely due to test drug or device.

7.5. Method, Frequency, and Time Period for Detecting Adverse Events and Serious Adverse Events

At appropriate intervals (e.g., at every study visit and telephone contact), patients should be assessed for TEAEs and SAEs. After the patient has had an opportunity to spontaneously mention any problems, the Investigator should inquire about TEAEs by asking a non-leading question such as the following:

1. “How are you feeling?”
2. “Have you had any medical problems since your last assessment/visit?”
3. “Have you taken any new medicines since your last assessment/visit?”

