8.1. ADVERSE EVENTS

AEs will be coded using MedDRA version 20.1.

AEs will be considered TEAE unless there is clear indication that the event occurred prior to the first dose of study drug. AEs present prior to study drug administration that increased in severity or relationship to study drug afterwards will also be classed as TEAEs.

All AEs that occur after the first dose of study drug will be considered to be 'treatment-

'emergent' with the exception of AEs that occur more than 7 days after the last dose of study drug.

Events with missing or partial dates will be handled such that in the absence of contradictory information an AE is treatment emergent (see Section 6.2).

Only TEAEs will be included in the summary tables.

An overall summary will present the number of subjects with:

- any TEAE*
- any TEAE considered as related to study drug (evaluated by the investigator as Related or severity not reported)*
- any serious TEAE*
- any serious TEAE considered as related to study drug*
- Maximum severity TEAEs of mild, moderate or severe; i.e. a subject with TEAEs at different intensities will be summarized at the most severe intensity
- Maximum severity TEAEs considered as related to study drug of mild, moderate or severe; i.e. a subject with TEAEs at different intensities will be summarized at the most severe intensity
- any TEAE leading to study drug discontinuation (i.e. TEAEs reported as having either an action taken as 'Drug Withdrawn') and/or Study Discontinuation*
- any TEAE considered as related study drug discontinuation (i.e. TEAEs reported as having either an action taken as 'Drug Withdrawn') and/or Study Discontinuation *
- any TEAE leading to death*

The table will also include the total number of TEAEs reported for those flagged (*). The total number of unique terms within subjects will also be presented for those flagged (*), counting each TEAE PT only once within each subject.

This overall summary will be presented for both the Safety and mITT populations.

This summary will also be produced using the Safety population for the following:

- the subgroups in Section 6.3
- those TEAEs with an onset up to the Month 2 visit (inclusive) and those with an onset after the Month 2 visit separately.

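### An inhaler fault that harms no one is reportable as an adverse event, and if rated Related it is tabulated as related to study drug

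*Protocol*

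**What the plan says.** **Device events.** Protocol 7.2 treats a fault in the inhaler as an event once the patient has tried to use it: "if the device malfunctioned or broke once use was attempted by the participant; it would be reportable as an AE". Consequences to the patient matter only for the further step of calling it an SAE. The same section defines device events more narrowly: "An Adverse Device Event (ADE) is defined as any untoward and unintended response to a medical device".

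**Adverse events.** Protocol 7.1 starts from "An AE is any untoward medical occurrence associated with the use of a drug in humans, whether or not considered drug related". It makes every AE after treatment a TEAE. Its list of what a TEAE does not include contains "Situations where an untoward medical occurrence has not occurred", with elective, social and convenience admissions as the examples.

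**Relatedness.** Protocol 7.4 asks one yes/no question, phrased in terms of study drug. The Related answer covers events "that the Investigator determines are most likely due to test drug or device".

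**Analysis.** SAP 8.1 has a row for "any TEAE considered as related to study drug", which takes in whatever the investigator rated Related. Its related summaries are all worded in terms of study drug, and none is restricted to device events. The safety endpoint in Protocol 3.2.2 and SAP 4.2 is worded for drug and device together. Protocol 8.7 lists Adverse Device Effects among the items to be summarized.

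**The concern.** Protocol 7.1 and 7.2 give different answers for one situation: the inhaler breaks on attempted use and the patient suffers nothing. Under 7.2 this is an AE. Under the general definition in 7.1 it is not, because nothing medical has happened.

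What happens next is the statistical problem. A fault recorded under 7.2 goes into TEAE incidence, which is the primary endpoint (Protocol 3.2.1, SAP 4.1). If it is rated Related because of the device, it also goes into tables whose label attributes it to the drug. A reader of the final report would take those tables as a measure of drug tolerability. Meanwhile, no planned table shows how the inhaler itself performed.

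**Working it through.** The plan states no figure to reproduce. The check is to follow one harm-free fault through the rules, then work out what one such patient does to the percentages.

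**Following the record**

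1. The inhaler breaks on attempted use and the patient is unharmed. Protocol 7.2: AE.
2. It happens during treatment. Protocol 7.1 makes an AE after treatment a TEAE. SAP 8.1 agrees for events after the first dose and up to 7 days after the last. Calling the fault an AE but not a TEAE is therefore not a way out.
3. Causality. In Protocol 7.4 the cause is the device, so Related is the natural answer, although the investigator must still give it.
4. Tabulation. SAP 8.1 counts Related as related to study drug. Nothing in 8.1 separates malfunction-only records.
5. A side route. The severity grades in Protocol 7.3 are written in terms of a symptom, and a harm-free fault has none. If severity is left blank, SAP 6.2.2 sets it to severe. The related row in SAP 8.1, as worded, also takes in events with severity not reported.

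**Effect of one patient**

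Inputs: Safety Population 121, made up of 55 Transition and 66 Add-On (SAP 5.2; 55 + 66 = 121). SAP 6.1 uses the analysis population as the denominator.

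Added incidence per patient whose only related event is a harm-free fault = 1/N:

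| Column | N | Added percentage points |
|---|---|---|
| Overall | 121 | 100/121 = 0.83 |
| Transition | 55 | 100/55 = 1.82 |
| Add-On | 66 | 100/66 = 1.52 |

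The any-TEAE row moves by the same amount only if the fault is the patient's sole TEAE of any kind. A patient who already has another related TEAE adds nothing to the related row.

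**Why the total cannot be stated**

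The documents give no malfunction rate. For illustration only, assume a rate p per use, one device use per dose, and all patients followed for 60 days: 4 × 60 = 240 uses. The chance of at least one fault is 1 − (1 − p)^240. If an assumed 50% of patients have a genuine related TEAE, independent of faults, the addition to related incidence is 0.5 times that chance.

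| Assumed p | At least one fault | Patients of 121 | Added points at 50% base |
|---|---|---|---|
| 0.001% | 0.24% | 0.3 | 0.1 |
| 0.01% | 2.4% | 2.9 | 1.2 |
| 0.1% | 21.3% | 25.8 | 10.7 |

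With base incidence varied from 30% to 70%, the addition runs from 0.07 to 14.9 points. The result depends almost entirely on the assumed rate, so it is not an estimate.

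**The case against.** The strongest reply is that 7.2 is the specific rule for the device and 7.1 the general rule for drugs. The examples beside the exclusion in 7.1 are all admissions, and nothing tells a site with a broken inhaler to prefer that exclusion to a direct instruction in the device section. This reading is fair. The documents do not state it, which is why the sections should be reconciled. If it is correct, every site records the fault, and the labelling problem remains in full.

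A second reply is that pooling drug and device causes is intended, because the safety endpoint is worded that way. That is correct, and it justifies counting device-caused events as related. It does not justify a row label that names only the drug. It is also true that the tables by preferred term would probably show a device fault under its own term, so it would not be hidden among cough or headache. The overall summary gives no such view.

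Three stronger readings are tempting, and the documents do not support them:

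- A reader might infer that some sites recorded faults and others did not, so that TEAE incidence cannot be interpreted. Nothing shows that sites differed.
- A reader might infer that unrecorded faults are lost. Protocol 7 limits recording to TEAEs and SAEs, and the device-event definition needs a response, so the inference is understandable. But Protocol 6.1.1 lists device events as an assessment in their own right. The eCRF and the Safety Management Plan, which might hold a device field, are not among the documents.
- A reader might build a count from the packaging, "as four capsules per bottle, with eight bottles and two DIs per box". That gives 8 × 4 = 32 capsules, 8 days per box at one capsule four times daily, one inhaler per 4 days and 60 inhalers by Day 240. An assumed failure rate of 0.1% to 0.5% per inhaler then gives 5.8% to 26% of patients, or 7 to 31 of 121. The failure rate has no source, and no replacement interval is stated. Doses of 125 and 150 µg use two capsules. Only 113 patients had the Month 2 visit. The count also takes no account of patients who already have a related TEAE.

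**Conclusion.** The concern holds in a limited form. Protocol 7.1 and 7.2 need to be reconciled on whether a fault without medical consequence is an AE. Whichever reading was intended, a harm-free fault recorded under 7.2 and rated Related under 7.4 is counted in the primary endpoint and reported in SAP 8.1 as related to study drug. That label is wrong for such a record and does not match the plan's own drug/device endpoint. The device summary promised in Protocol 8.7 is also missing from SAP 8.1.

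The size per affected patient is exact: 0.83 points overall, 1.82 in Transition or 1.52 in Add-On. The total is unknown and could be nil, since no document shows that any malfunction was recorded. The conclusion assumes that relatedness was collected as Protocol 7.4 describes, with no separate device field. The study is open-label and descriptive with no formal hypothesis test, so the consequence is a misdescribed safety table, not a wrong inference.

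**What to change.** In SAP 8.1, before database lock:

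- Keep all AE records as collected. Dropping malfunction-only records from the primary tables would remove events that 7.2 defines as AEs and could make the final tables inconsistent with the Month 2 report.
- Flag records that describe only a device fault with no medical occurrence.
- Show the overall TEAE and related-TEAE summary with and without the flagged records.
- Relabel the pooled related rows as related to study drug or device, wherever they appear.
- Add the Adverse Device Effects summary, with malfunctions on a separate line.

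In the protocol, for any data collection that continues, state in 7.2 how the malfunction rule stands to the definition in 7.1. In the clinical study report, say that any fault left unrecorded because a site applied 7.1 cannot be recovered.

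The cost is a review of AE terms for 121 patients and one small table. A new eCRF page would come too late for most of the data, as enrolment is complete and Month 2 has been reported.

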7.2.1. Unanticipated Adverse Device Effects

Unanticipated adverse device effect is any serious adverse effect on health or safety or any life-threatening problem or death caused by, or associated with, a device, if that effect, problem, or death was not previously identified in nature, severity, or degree of incidence in the investigational plan or application (including a supplementary plan or application), or any other unanticipated serious problem associated with a device that relates to the rights, safety, or welfare of participants.

All unanticipated adverse device effects must be reported by the Investigator to the Sponsor within 3 days from identification or awareness of the event. Investigators are responsible for preparing and submitting complete, accurate, and timely reports to the reviewing IRB of any unanticipated adverse device effect occurring during an investigation as soon as possible, but in no event, later than 10 working days after they first learn of the effect.

Any device that is associated with an unanticipated adverse device effect should be collected from the patient in accordance with the same procedures as any other used device (i.e., device accountability and marked for destruction).

If the Sponsor determines that an unanticipated adverse device effect, as reported by an Investigator, presents an unreasonable risk to the subject, the Sponsor shall terminate all investigations or parts of investigations presenting that risk as soon as possible.

7.3. Severity of TEAEs/SAEs

The severity (mild, moderate, or severe) of each TEAE/SAE must be assessed by the Investigator, or designee. The following criteria should be considered when assessing severity:

- Mild The symptom is barely noticeable to the patient and does not influence performance or functioning.
- Moderate The symptom is of sufficient severity to make the patient uncomfortable, and performance of daily activities is influenced. Treatment for the symptom may be needed.
- Severe The symptom causes severe discomfort. Treatment for the symptom may be necessary.

7.4. Assessment of Relatedness to Study Drug or Device

The Investigator will assess each TEAE and ADE for causality based on their medical judgment and the observed symptoms associated with the event. Each TEAE and ADE will be assessed as related or unrelated to study drug based on the following criteria:

- Unrelated This category applies to those TEAEs and ADEs that the Investigator determines are most likely due to extraneous causes (disease, environment, etc.) and does not follow a reasonable temporal relationship.
- Related This category applies to those TEAEs and ADEs that the Investigator determines are most likely due to test drug or device.

7.5. Method, Frequency, and Time Period for Detecting Adverse Events and Serious Adverse Events

At appropriate intervals (e.g., at every study visit and telephone contact), patients should be assessed for TEAEs and SAEs. After the patient has had an opportunity to spontaneously mention any problems, the Investigator should inquire about TEAEs by asking a non-leading question such as the following:

1. “How are you feeling?”
2. “Have you had any medical problems since your last assessment/visit?”
3. “Have you taken any new medicines since your last assessment/visit?”

7.6. Reporting AEs and SAEs

7.6.1. Reporting Adverse Events

AEs occurring from when the patient signs the Informed Consent Form (ICF) until the last study event will be recorded. All AEs and SAEs occurring prior to the first inhalation of LIQ861 will be recorded in the medical history. Also, any sign, symptom, or disease present before the first inhalation of LIQ861 are considered AEs only if they have worsened after the first inhalation of LIQ861.

If the investigator detects an AE in a study patient after the last scheduled follow-up visit and considers the event related to treatment with LIQ861, the investigator should report it to the Sponsor's Medical Monitor.

The investigator should report all AEs on the AE page(s) of the eCRF and source documents, regardless of seriousness, severity, and causality. Whenever possible, an AE will be reported using a diagnostic term (e.g., "common cold" or "upper respiratory infection" rather than "runny nose, cough, mild fever") and should be described with the attributes described in terms of severity (Section 7.3) and relatedness (Section 7.4).

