6.2.3. Baseline – PK Sub-Study (Visit 2; Day 1 & Day 2)

The description of assessments in this section is intended **ONLY** for patients that are enrolled in the PK Sub-Study. Patients that are **NOT** enrolled in the PK Sub-Study should follow the assessments described in Section [6.2.2](#).

Day 1

The following assessments are to be completed at Baseline and prior to Tyvaso administration on Day 1:

- Eligibility re-assessment

- Brief physical examination
- Vital signs (temperature, blood pressure, respiratory rate, and heart rate) collected after the patient has been upright and rested for at least 5 minutes
- Weight
- Venous blood for clinical laboratory tests, including NT-proBNP
- Urine pregnancy test (for all females of child bearing potential, Day 1 only)
- 6MWT
- NYHA Functional Class Assessment
- Assessment of PAH Symptoms
- Prior medications
- Record time of last dose of inhaled treprostinil
- Plasma for baseline PK measurement (must be taken before Tyvaso administration, within 30 minutes of dose administration)
- Final dose of Tyvaso (after all other predose assessments)
 - Note that this must be the first dose of the day. If the subject has taken Tyvaso prior to arrival at the clinic, the PK sub-study should not be conducted or the visit should be rescheduled.

The following assessments are to be completed after Tyvaso administration on Day 1, but before the first dose of LIQ861 is administered:

- Plasma for PK measurements at 5, 10, 15, 20, 25, 30, 45, 60, 90, 120, and 180 minutes and 4 hours after Tyvaso administration. Actual times of blood collection for each timepoint must be recorded.
- Adverse Events
- Concomitant medications
- Venous blood for clinical laboratory tests at 4 hours after Tyvaso administration
- MLWHF questionnaire
- DPI Training

The second treprostinil dose of the day should be the first administration of LIQ861. The following assessments are to be completed after the first dose of LIQ861 is administered:

- Treatment-Emergent Adverse Events
- Concomitant medications
- Inhalation Device User Survey
- Study Drug Dispensation
- Schedule Next Visit

Day 2

The following assessments are to be completed at Baseline and prior to study drug administration on Day 2:

- Treatment-Emergent Adverse Events
- Eligibility re-assessment
- Brief physical examination
- Vital signs (temperature, blood pressure, respiratory rate, and heart rate) collected after the patient has been upright and rested for at least 5 minutes

- Weight

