7. ADVERSE EVENTS

The Investigator is responsible for the detection and documentation of events meeting the definition of an AE or SAE as provided in this protocol. Only Treatment-Emergent AEs (TEAEs) and SAEs (occurring after the first inhalation of LIQ861, or Tyvaso in the PK sub-study, through the appropriate follow-up period) will be recorded in this study.

Definitions and terminology relevant to IND Safety Reports, as referenced in the U.S. Code of Federal Regulations, are addressed below.

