7.6.5. Clinical Laboratory Abnormalities and Other Abnormal Assessments as TEAEs and SAEs

The Investigator should exercise his or her medical and scientific judgment in deciding whether an abnormal laboratory finding or other abnormal assessment is clinically relevant.

Abnormal laboratory findings (e.g., clinical chemistry, hematology) or other abnormal assessments (e.g., vital signs) that are judged by the Investigator as clinically relevant must be recorded in the medical history or as TEAEs or SAEs if they meet the definition of an adverse event. Clinically relevant abnormal laboratory findings or other abnormal assessments that are detected after the first inhalation of LIQ861, or that are present before administration of LIQ861 but worsen after the first inhalation of LIQ861, should be assessed for AE criteria.

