- This table is for assessments in the PK Sub-Study. For Day 1 assessments for patients that are not in the PK Sub-Study, see the Study T&E Table ([above](#))
- A full PE will be conducted on Visit 1; a brief PE will be conducted during Visit 2.
- Height does not need to be assessed at Visit 2.
- Vital signs, temperature, blood pressure, respiratory rate, and heart rate (blood pressure, respiratory rate, and heart rate will be measured after the patient has been upright and rested for at least 5 minutes).
- Obtain venous blood for clinical laboratory tests at predose and 4 hours post-dose on Day 1 and Day 2.
- Blood for clinical labs and PK collected in the 4th hour after dosing should be obtained prior to administration of the first dose of LIQ861 on Day 1 and prior to administration of the second dose of LIQ861 on Day 2.
- Females of childbearing potential only.
- The Inhalation Device User Survey should be administered after administration of LIQ861.
- Patients should receive device training prior to the first dose of LIQ861 on Day 1 and Day 2. Timing in relation to dose administration is not critical.

- j. For PK sub-study only: Collect blood for measurement of treprostinil concentrations predose (within 30 minutes before dosing), and at 5, 10, 15, 20, 25, 30, 45, 60, 90, 120, and 180 minutes and 4 hours after study drug administration. Record actual times of blood collection for each timepoint.
- k. Adverse events will be collected after administration of Tyvaso.

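### Events between the Day 1 Tyvaso dose and the first LIQ861 inhalation in the PK sub-study have conflicting recording rules, and the SAP gives them no display of their own

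*Protocol*

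**What the plan says.** Three places in the protocol start AE recording at Tyvaso for PK sub-study patients:

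- Section 7 limits recording to TEAEs and SAEs "occurring after the first inhalation of LIQ861, or Tyvaso in the PK sub-study, through the appropriate follow-up period".
- Section 6.2.3 has a Day 1 list introduced by "The following assessments are to be completed after Tyvaso administration on Day 1, but before the first dose of LIQ861 is administered". Adverse events and a 4-hour laboratory draw are both on it.
- The PK sub-study schedule in Appendix 1 carries the footnote "Adverse events will be collected after administration of Tyvaso".

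Two places start at LIQ861 and make no exception for the sub-study:

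- Section 7.6.1: "All AEs and SAEs occurring prior to the first inhalation of LIQ861 will be recorded in the medical history". It adds that signs, symptoms or disease already present then "are considered AEs only if they have worsened after the first inhalation of LIQ861".
- Section 7.6.5 applies AE criteria to clinically relevant abnormal findings "detected after the first inhalation of LIQ861, or that are present before administration of LIQ861 but worsen after the first inhalation of LIQ861".

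Section 7.1 defines a TEAE by treatment with the investigational product and does not mention Tyvaso.

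The SAP sets its default in Section 8.1: "AEs will be considered TEAE unless there is clear indication that the event occurred prior to the first dose of study drug". Only TEAEs enter its AE summary tables. Under SAP 6.1, every table shows Overall and the Transition and Add-On groups, so no column covers the Tyvaso period. The protocol synopsis, by contrast, foresaw AE displays by dose level of one or both drugs.

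**The concern.** A site cannot follow both sets of rules. An event two hours after the Day 1 Tyvaso dose is a recordable AE or SAE under Section 7 and medical history under Section 7.6.1. Sites may resolve the conflict differently, and the data would then mix two conventions.

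Two things are at stake. One is visibility: an event soon after a supervised treprostinil dose could end up among pre-existing conditions. The other is attribution: if the event is on the AE page but cannot be placed before LIQ861, it enters the LIQ861 TEAE tables and so the primary endpoint. That endpoint is grouped by dose level and time on drug, and an event that precedes LIQ861 has neither for LIQ861.

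**Working it through.** The check is mainly a comparison of text. There is no plan figure to reproduce.

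**1. The window.** Protocol 3.1 and Appendix 2 place the Tyvaso dose first on Day 1, with PK sampling for 4 hours and LIQ861 as the second treprostinil dose that day. Both products therefore fall on the same calendar date.

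**2. A clinical event in the window.**
- Sections 7 and 6.2.3 and the schedule footnote: record as an AE or SAE.
- Section 7.6.1: record in medical history, and treat as an AE only if it worsens after LIQ861.

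**3. A laboratory finding in the window.** The 4-hour sample is scheduled for every sub-study patient and, by an Appendix 1 footnote, is drawn before LIQ861.
- Section 6.5: every clinically significant value is recorded as an AE.
- Section 7.6.5: AE criteria apply if the finding is detected after LIQ861, or was present before and worsens. Whether a sample drawn before LIQ861 but read afterwards counts as detected afterwards is not stated.

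**4. What the SAP does with such an event.**
- *Onset time known and before LIQ861:* if study drug means LIQ861, the event is not a TEAE and reaches no AE summary table. SAP 6.1 promises listings of all data and SAP 8.1 a listing of serious AEs, but neither labels a Tyvaso period.
- *Onset date only, Day 1:* the date does not show which product came first. Without other evidence the default in SAP 8.1 makes the event a TEAE. SAP 6.2.3 imputes dates only and has no rule for a missing time.
- *Filed as medical history:* the event is outside the AE analysis.

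A patient with an event after Tyvaso who never inhales LIQ861 is also outside the Safety Population (SAP 5.2).

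**5. Size of the window.** Inputs: at least 18 patients (Protocol 8.1; SAP 3.2 gives 18), about 4 hours, and 121 Safety subjects including 55 Transition (SAP 5.2).
- 18 × 4 h = 72 patient-hours = 3 patient-days.
- 18/121 = 14.9%; 18/55 = 32.7%. These are shares of patients passing through the window, not changes in incidence.

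**6. Illustration only.** The documents give no event rate for this window. Assume that a fraction p of the 18 has an event there. Affected patients = 18p; shift in Overall incidence = 18p/121; shift in Transition incidence = 18p/55; chance of at least one affected patient = 1 − (1 − p)^18.
- p = 5%: 0.9 patients, 0.7 points Overall, 1.6 points Transition, 60% chance of at least one.
- p = 30%: 5.4 patients, 4.5 points Overall, 9.8 points Transition, 99.8% chance of at least one.

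For each p the shifts are ceilings. They require every affected patient to be misattributed and to have no other TEAE in the whole study.

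**The case against.** A reader might infer that a serious event after Tyvaso would go unreported. The documents do not support that. Section 7.6.1 itself opens by recording AEs from consent and later requires all AEs on the AE page regardless of seriousness. Section 7.6.2 sets 24-hour SAE timelines with no LIQ861 start point. The two provisions written for PK Day 1 both collect AEs after Tyvaso, so a site following them would record the event. This stands. What remains is a risk from conflicting instructions.

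A reader might also infer that Tyvaso reactions are routinely counted in the LIQ861 primary endpoint. This too goes beyond the text. SAP 3.4 and 3.5 describe only LIQ861 as the treatment given, and SAP 5.2 ties the Safety Population to it, so study drug in SAP 8.1 most naturally means LIQ861. SAP 8.1 computes AE duration from date and time, so onset times are expected. Patients are in clinic with 12 timed post-dose samples. Treating a genuinely uncertain event as a TEAE is a conservative default, not an error.

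The 14.9% and 32.7% might be read as impact, which they are not. Subjects are counted once per SOC or SOC/PT, the patients were stable on Tyvaso for at least 3 months, and no hypothesis is tested.

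Finally, the remedy is late: SAP 2, 4.3 and 5 say that Month 2 and PK results are already reported. A protocol edit cannot change how past Day 1 events were collected. The final report can still classify them consistently and show them.

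**Conclusion.** The contradiction is real and lies in current text: Sections 7 and 6.2.3 and the schedule footnote against Sections 7.6.1 and 7.6.5. It affects events and planned 4-hour laboratory findings in at least 18 patients.

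Non-reporting is a possibility, not an established consequence. Counting a Tyvaso event against LIQ861 is likely only where the Day 1 onset time is missing. Where the time is known, the event would appear in no AE summary table.

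The effect on overall incidence is probably small and cannot be quantified from the documents. This rests on reading study drug in the SAP as LIQ861 and on a window of about 4 hours. The point is minor, worth correcting for consistent classification and visibility in the final report.

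**What to change.** - **Protocol:** reconcile Sections 7, 7.6.1 and 7.6.5 so that post-Tyvaso events and abnormal findings in the PK sub-study are recorded as AEs or SAEs and not as medical history.
- **SAP 8.1:** state that LIQ861 TEAEs start at the first LIQ861 inhalation, using onset time on Day 1, and say how a Day 1 event without a time is handled.
- **Display:** list or tabulate events between the Tyvaso dose and the first LIQ861 inhalation separately, labelled as the Tyvaso period.

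SAP 2 allows amendment before database lock. The cost is a few sentences and a little extra analysis work. Data already collected may lack onset times, and some events may already be in medical history. Checking the sub-study patients' Day 1 entries would show how many are affected.
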